8.1.6. Clinician/Participant Rated Response to Therapy

The clinician and the participant will be asked to rate the response to therapy at the visits specified in the Time and Events schedule relative to the participant's asthma at Visit 2 (immediately prior to the first dose of mepolizumab). This is an overall evaluation of response to treatment, conducted separately by the investigator and the participant using a rating scale. In this rating scale, a seven-point scale score is used with the following definitions:

- 2 = ccl3 = ccl
- 4 = cci
- 5 = CCI
- 6 = CCI
- 7 = ccl

The clinician or participant will indicate their response on a paper questionnaire which will be transcribed into the eCRF by study designated site staff.

8.1.7. Work Productivity and Activity Impairment Questionnaire: General Health (WAPI-GH)

Asthma has a substantial effect on lost days of works, with millions of days being lost each year (Catley, 2011). Furthermore, asthma results in lost productivity due to decreased effectiveness while working (Wilson, 2012). The WPAI-GH is a self or interviewer administered tool comprised of 6 questions which address absenteeism, presenteeism (reduced effectiveness while working), overall work productivity loss (absenteeism plus presenteeism), and activity impairment. This validated tool captures data from the past 7 days. WPAI-GH outcomes are scored as impairment percentages, with a higher percentage indicating greater impairment and less productivity (Reily Associates, 2018).

Participants will initially complete the paper questionnaire, and then the study designated site staff will transcribe the information into the eCRF.

8.2. Safety Assessments

Planned time points for all safety assessments are provided in the SoA.

8.2.1. Safety Endpoints

- Adverse Events, including both systemic (i.e., allergic/IgE-mediated and nonallergic) and local injection site reactions reported throughout the 24-week treatment period.
- Assessments include Physical examination, vital signs, Electrocardiogram, and laboratory evaluation.

8.2.2. Physical Examinations

• A complete physical examination will include, at a minimum, assessments of the Skin, Cardiovascular, Respiratory, Gastrointestinal and Neurological systems. Height and weight will also be measured and recorded.

- A brief physical examination will include, at a minimum, assessments of the abdomen (liver and spleen).
- Investigators should pay special attention to clinical signs related to previous serious illnesses.
- Detailed nasal examination for presence or absence of nasal polyps will be performed.

8.2.3. Vital Signs

- Oral/ Axillary temperature, pulse rate, respiratory rate, and blood pressure will be assessed.
- Blood pressure and pulse measurements will be assessed in sitting position with a completely automated device. Manual techniques will be used only if an automated device is not available.
- Blood pressure and pulse measurements should be preceded by at least 5 minutes of rest for the participant in a quiet setting without distractions (e.g., television, cell phones).
- Vital signs (to be taken before blood collection for laboratory tests) will consist of 1 pulse and 3 blood pressure measurements (3 consecutive blood pressure readings will be recorded at intervals of at least 1 minute). The average of the 3 blood pressure readings will be recorded on the CRF.

8.2.4. Electrocardiograms

- Electrocardiogram measurements will be made after the participant has rested in the supine position for 5 minutes. The ECG should be obtained before lung function testing followed by other study procedures. Collection shortly after a meal or during sleep should be avoided since QT prolongation can occur at these times.
- A single twelve-lead ECG will be obtained at each timepoint specified in the Schedule of Activities (Section 1.3). If a routine single ECG demonstrates a prolonged QT interval, obtain two more ECGs over a brief period (eg: 5-10 mins), and then use the averaged QTc values of the three ECGs to determine whether the patient should be discontinued from the study.
 - Refer to Section (Section 7.1.2) for QTc withdrawal criteria.
- Paper traces are required to be maintained at the site with other source documents.

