7. DISCONTINUATION OF STUDY INTERVENTION AND PARTICIPANT DISCONTINUATION/WITHDRAWAL

7.1. Discontinuation of Study Intervention

Participants who permanently stop study intervention are not required to withdraw from the study. If for any reason a participant must permanently stop study intervention every effort should be made by the PI/staff to keep the subject in the study to collect important efficacy and safety data.

See the SOA for data to be collected at the time of discontinuation of study intervention.

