7.1.2. QTc Stopping Criteria

• QTc(f) QT correction (Fredericia) formula *must* be used for each individual participant to determine eligibility for and discontinuation from the study. This formula may not be changed or substituted once the participant has been enrolled.

The QTc should be based on the average of triplicate ECG readings obtained over a brief (e.g., 5-10 minute) recording period.

- QTc stopping criteria are
 - QTc(F)>500 msec or uncorrected QT>600 msec
 - Change from baseline: QTc(F) > 60 msec
 - For patients with underlying bundle branch block, follow the discontinuation criteria listed below:

ъ	1.	ОТ	• 41	n	11	D.	4.		• 41	D	11	
												209682

Baseline QTc (F) with Bundle Branch Block	Discontinuation QTc (F) with Bundle Branch Block
< 450 msec	> 500 msec
450 – 480 msec	≥ 530 msec

See the SoA for data to be collected at the time of intervention discontinuation and end of study and for any further evaluations that need to be completed.

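### The repeat-ECG trigger in Protocol 8.2.4 is undefined and not aligned with the QTc stopping criteria in 7.1.2, and both sections word the consequence as leaving the study, against 7.1 and 7.2

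*Protocol*

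**What the plan says.** Protocol 7.1.2 prescribes the Fridericia correction and then states: "The QTc should be based on the average of triplicate ECG readings obtained over a brief (e.g., 5-10 minute) recording period". Its criteria include an absolute one, "QTc(F)>500 msec or uncorrected QT>600 msec", and a separate relative one, "Change from baseline: QTc(F) > 60 msec". Participants with bundle branch block have their own table of limits.

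Protocol 8.2.4 schedules one ECG at each timepoint. In the Schedule of Activities these are screening, Weeks 0, 8, 16 and 24, and the IP discontinuation visit. It goes on: "If a routine single ECG demonstrates a prolonged QT interval, obtain two more ECGs over a brief period". The site is then to "use the averaged QTc values of the three ECGs to determine whether the patient should be discontinued from the study". The section points to 7.1.2 for the criteria themselves.

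On the consequence, 7.1.2 is a subsection of 7.1, which deals with stopping study intervention. Section 7.1 opens: "Participants who permanently stop study intervention are not required to withdraw from the study". It asks sites to try to retain these participants, and 7.2 repeats both statements. Yet 7.1.2 describes QTcF as the measure used "to determine eligibility for and discontinuation from the study", and 8.2.4 also speaks of discontinuation from the study.

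SAP 11.6 counts participants with a rise above 60 ms at each visit, alongside absolute categories of >450, >480 and >500 ms. It uses a mean only where three ECGs were recorded.

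**The concern.** The stopping criteria need a three-ECG mean, but the only instruction to obtain one depends on a phrase that the protocol does not define. The phrase has no threshold, refers to QT while the criteria rest mainly on QTcF, and is not tied to change from baseline. A site could meet a reading that satisfies the change criterion and find nothing in 8.2.4 ordering the repeats. It would then have to judge the criterion on a single reading, take repeats on its own initiative, or leave the criterion unjudged. Sites may differ in which they do, in a multi-centre study whose primary objective is safety and which has no data monitoring committee.

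The second issue is what happens once a criterion is met. If sites read the wording as leaving the study, follow-up ends early. The supplementary adverse-event estimand and all the secondary efficacy estimands use a treatment-policy strategy for stopping treatment, as do the summaries of ECG, vital signs, laboratory and immunogenicity data in Protocol 9.4.1. All of these need data after treatment stops.

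**Working it through.** The documents state no figure to reproduce here. The check compares the sections and adds simple threshold arithmetic.

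**Step 1. Each 7.1.2 criterion against the 8.2.4 trigger.**

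| Criterion in 7.1.2 | Scale | Does a 'prolonged QT interval' capture it? |
|---|---|---|
| QTcF above 500 msec | corrected, absolute | Yes, if the trigger is a QTcF limit no higher than 500; not assured if it is uncorrected QT |
| Uncorrected QT above 600 msec | uncorrected, absolute | Yes, if the trigger is a QT limit no higher than 600 |
| QTcF rise above 60 msec | corrected, relative | Only if 'prolonged' includes prolongation against baseline, or if the baseline is high enough |
| Bundle branch block limits | corrected, by baseline band | Depends on the limit chosen |

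**Step 2. Size of the gap for the change criterion, if 'prolonged' is an absolute QTcF limit.** Let *b* be baseline QTcF, *v* the on-study value, and *T* the limit above which a reading counts as prolonged. The criterion is met without a trigger when *v* − *b* > 60 and *v* ≤ *T*, which is possible whenever *b* < *T* − 60. The protocol gives no *T*. As an assumption, take the three SAP 11.6 categories:

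- *T* = 450: 450 − 60 = 390, so any baseline below 390. Example: 445 − 380 = 65, with 445 < 450. At the edge: 389 to 450 is +61.
- *T* = 480: 480 − 60 = 420, so any baseline below 420. At the edge: 419 to 480 is +61.
- *T* = 500: 500 − 60 = 440, so any baseline below 440. At the edge: 439 to 500 is +61.

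All these baselines pass the 450 msec entry limit in Exclusion Criterion 12.

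**Step 3. The same trigger read relative to baseline.** If a rise of more than 60 msec itself counts as prolonged, every reading in Step 2 prompts repeats and the gap is zero. No section states this reading.

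**Step 4. The trigger read literally as uncorrected QT.** By Fridericia, QT = QTcF × (60/heart rate)^(1/3). Take QTcF 501 msec, just over the absolute criterion, at illustrative heart rates:

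- 60 bpm: 501 × 1 = 501 msec.
- 90 bpm: 501 × (60/90)^(1/3) ≈ 438 msec.
- 100 bpm: 501 × (60/100)^(1/3) ≈ 423 msec.

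On this reading even the absolute QTcF criterion could be met while the QT does not look prolonged.

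**Step 5. The baseline side of the change.** The screening and Week 0 ECGs are also single unless prolonged. If repeats are triggered later, the change is a three-ECG mean minus a single reading. Section 7.1.2 does not say whether that is intended. It also covers eligibility, while 8.2.4 mentions the mean only for discontinuation.

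**Step 6. The consequence.** Sections 7.1.2 and 8.2.4 agree with each other in naming the study. They differ from the heading that 7.1.2 sits under and from the retention rule in 7.1 and 7.2. Section 7.1.2 closes by referring to data collected at intervention discontinuation, so it uses both terms. Between the first dose and the last (Week 20), scheduled ECGs fall at Weeks 8 and 16. A participant taken out of the study at those visits would lose up to 24 − 8 = 16 or 24 − 16 = 8 weeks of follow-up.

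**The case against.** The strongest reply is that the two sections form one workable sequence: a routine single ECG, two more if it looks prolonged, then the 7.1.2 criteria applied to the mean. They agree on three ECGs and on the 5-10 minute period, and 8.2.4 cross-refers to 7.1.2. Because 7.1.2 includes the change criterion, an investigator could fairly take a rise above 60 msec as prolongation. Nothing in 8.2.4 forbids extra ECGs, and 7.1.2 itself calls for the mean. The 450 msec in the example is an entry limit that 8.2.4 does not cite.

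Most of this stands. A reader might infer a flat contradiction between the sections, or that the change criterion will go unassessed. The documents support neither: the gap exists only on an absolute (or uncorrected) reading of 'prolonged'. What remains is that the protocol does not choose between the readings, so a site following 8.2.4 literally may have no mean on which to judge a listed criterion.

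A reader might also infer that 8.2.4 and 7.1.2 disagree about study versus treatment discontinuation. They do not, since both say the study. The tension is with 7.1 and 7.2. Section 7.2 does list an ECG over-read abnormality among possible withdrawal reasons, so the documents leave the intended consequence open.

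The impact also has limits. The primary estimand counts events only to 28 days after the last dose, so it is affected only if someone leaves before those 28 days have passed. SAP 11.6 will show rises above 60 ms after the fact, though a summary table is not a stopping decision.

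**Conclusion.** The point holds as a misaligned trigger and an inconsistent consequence, not as two opposing safety rules. Under the assumed limits of 450, 480 or 500 msec, the change criterion can be met without repeats being ordered for baselines below 390, 420 or 440 msec respectively. Under a baseline-relative reading it cannot. How many participants would be affected cannot be derived from the documents. Withdrawal from the study on these grounds would cost at most 16 weeks of follow-up for a participant stopping at Week 8 and 8 weeks for one stopping at Week 16. The loss would fall mainly on the supplementary safety and secondary efficacy estimands. It is worth correcting because safety is the primary objective and the remedy is small.

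**What to change.** Reconcile Protocol 7.1, 7.1.2, 7.2 and 8.2.4 so that they state the same thing on three matters:

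1. What finding triggers repeat ECGs, on which scale (QT or QTcF), with the trigger covering every criterion listed in 7.1.2, including change from baseline.
2. How many ECGs lie behind the on-study value and behind the baseline value, and whether the mean also applies to eligibility.
3. Whether meeting a criterion means stopping study intervention or leaving the study, in the same terms throughout.

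Which thresholds and which clinical rule apply is for the sponsor's medical team. The cost is protocol wording. The SAP's ECG summaries need no new method, although a sentence in SAP 11.6 saying how many ECGs underlie the baseline would match item 2. If participants have already been assessed under the present text, the study report should say which reading sites used.

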8.2.5. Steroid withdrawal examination review, where applicable

• Assessment of steroid withdrawal (i.e. the signs and symptoms of adrenal insufficiency such as fatigue, lassitude, weakness, nausea and vomiting, and hypotension) will be performed as outlined in the SoA.

8.2.6. Clinical Safety Laboratory Assessments

- Refer to Appendix 2 for the list of clinical laboratory tests to be performed and to the SoA for the timing and frequency.
- The investigator must review the laboratory report, document this review, and record any clinically relevant changes occurring during the study in the AE section of the CRF. The laboratory reports must be filed with the source documents. Clinically significant abnormal laboratory findings are those which are not associated with the underlying disease, unless judged by the investigator to be more severe than expected for the participant's condition.
- All laboratory tests with values considered clinically significantly abnormal during participation in the study or within 7 days after the last dose of study intervention should be repeated until the values return to normal or baseline or are no longer considered significantly abnormal by the investigator or medical monitor.
- If such values do not return to normal/baseline within a period of time judged reasonable by the investigator, the aetiology should be identified and the sponsor notified.
- All protocol-required laboratory assessments, as defined in Appendix 2, must be conducted in accordance with the laboratory manual and the SoA.

8.2.7. Suicidal Ideation and Behaviour Risk Monitoring

This is not applicable to this study.

8.3. Adverse Events and Serious Adverse Events

The definitions of an AE or SAE can be found in Appendix 3.

The following adverse events of special interest will have customized AE and SAE pages in the eCRF:

- Systemic reactions
- Local injection site reactions

In addition, the investigator will be requested to assess events they consider systemic reactions against diagnostic criteria of anaphylaxis, and record in the CRF whether an event met the diagnostic criteria for anaphylaxis as outlined by the Second Symposium on Anaphylaxis [Sampson, 2006] and in Appendix 7

The investigator and any qualified designees are responsible for detecting, documenting, and reporting events that meet the definition of an AE or SAE and remain responsible for following up AEs that are serious, considered related to the study intervention or the study, or that caused the participant to discontinue the study intervention (see Section 7).

8.3.1. Time Period and Frequency for Collecting AE and SAE Information

- All SAEs will be collected from the start of intervention until the end of study visit at the time points specified in the SoA (Section 1.3). However, any SAEs assessed as related to study participation (e.g., study intervention, protocol-mandated procedures, invasive tests, or change in existing therapy) will be recorded from the time a participant consents to participate in the study.
- All AEs will be collected from the start of intervention until the end of study visit at the time points specified in the SoA (Section 1.3).
- Medical occurrences that begin before the start of study intervention but after obtaining informed consent will be recorded on the Medical History/Current Medical Conditions section of the case report form (CRF) not the AE section.
- All Initial SAEs will be recorded and reported to the sponsor or designee immediately and under no circumstance should this exceed 24 hours of occurrence, as indicated in Appendix 3. The investigator will submit any updated SAE data /follow-up information to the sponsor within 24 hours of site awareness.
- Investigators are not obligated to actively seek AEs or SAEs after the conclusion of the study participation. However, if the investigator learns of any SAE, including a death, at any time after a participant has been discharged from the study, and he/she considers the event to be reasonably related to the study intervention or study participation, the investigator must promptly notify the sponsor.

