3. OBJECTIVES AND ENDPOINTS

Objectives	Endpoints
Primary	*
To evaluate the safety, and tolerability of mepolizumab in participants with severe refractory asthma with elevated eosinophils	The primary estimand will be defined by the following: Endpoints: Incidence of on-treatment adverse events (AEs), serious adverse events (SAEs) and adverse events of special interest (AESIs)
	 Summary measure: Counts and percentages for incidence of at least one AE will be summarised overall, by system organ class and by preferred term
	 Population of interest: Severe refractory asthma patients in India with elevated eosinophils
	Key intercurrent events:Discontinuation of treatment (for any reason)
	 Strategy for intercurrent events: While on-treatment strategy will be used for treatment discontinuation. This will estimate the percentage of participants experiencing an AE, while receiving treatment. AEs will be defined as on-treatment between the first dose up to and including 28 days following the last dose of mepolizumab.
	A supplementary estimand will be defined using identical properties as for the primary estimand (summary measure, population of interest and key intercurrent events), however this supplementary estimand will report all AEs regardless of the discontinuation of study treatment. Endpoints: Incidence of AEs and SAEs
	 Strategy for intercurrent events: Treatment policy strategy will be used for treatment discontinuation. This summary will therefore be inclusive of all on-treatment and post-treatment AEs.
Secondary	
To evaluate the efficacy of mepolizumab in participants	The following secondary estimand is defined by the following:

Objectives	Endpoints
with severe refractory asthma	Endpoints:
with elevated eosinophils	 Number of clinically significant exacerbations (including exacerbations requiring hospitalization or ED visits) Number of exacerbations requiring hospitalization or ED visits Number of exacerbations requiring hospitalization Summary measure: Rate ratio comparing events/year during the 24-week follow-up period compared to the 12 months prior to screening Population of interest: Severe refractory asthma patients in India with elevated eosinophils Key intercurrent events: Discontinuation of treatment (for any reason)
	 Strategy for intercurrent events: Treatment policy strategy will be used for treatment discontinuation. This will estimate the treatment effect over the 24 week study period regardless of treatment discontinuation.

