The participant should be informed of the home healthcare plan and any potential risks associated with home visits and telemedicine. The participant must sign an informed consent form specific to home healthcare.

IRB/Ethics committee should be informed of the introduction of home healthcare in the study. The committee should approve the home healthcare plan and the process should be documented in study files.

Study Intervention

The home healthcare personnel will be responsible for administering the study IP (at the discretion of the investigator) according to procedures detailed in the protocol.

Protocol Defined Procedures/Visits:

- Study participants in the Treatment Period of the study (Visit 2 to Visit 8 should be contacted by sites at each scheduled study visit to collect the following:
 - o SAEs
 - o AEs
 - Concomitant medication

Note: the secondary objective of the study is to evaluate the efficacy of mepolizumab in participants with severe refractory asthma with elevated eosinophils. To evaluate the efficacy, the spirometry assessments "prebronchodilator FEV1 and post-bronchodilator FEV1" will be conducted. If the patient cannot come to site, the spirometry assessments can be conducted at home. It is the collective responsibility of Sponsor, site, and CRO to ensure that spirometers are available to conduct the home spirometry assessments and adequate training of the study personnel to conduct the assessments using all precautions and safety measures.

- The investigator shall contact their participants and intimate about the necessary precautions to ensure safety and wellbeing of the patients when encouraging them to visit the hospital. Investigator/designee staff need to stay in contact with the subject to ensure the end of study visit is completed within the prescribed window period (±7 Days).
- Where applicable country and local regulations (India) and infrastructure for home healthcare allows, home healthcare may take place at a location other than the clinical trial site to perform study assessments, which may include collection of blood and urine samples, ECG, spirometry, measurement of vital signs and weight, and preparation and administration of study drug (at the discretion of the Investigator). It is the responsibility of the investigator to inform Sponsor/CRO when this occurs and to document in source notes.

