7.2.4. Treatment Period

- Pre-treatment period = Date of Screening to Date of first dose minus 1
- On-treatment period = Date of first dose to Date of last dose plus 28 days inclusive
- Post-treatment period = End of last dose plus 29 days to End of study date

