7.2.8. Common Calculations

Each subject's age will be calculated based on their date of birth relative to the date of the screening visit. Where only a subject's year of birth is collected, their date of birth will be imputed with 30th June (30 Jun YYYY).

Body Mass Index (kg/m^2) = Weight $(kg)/Height (m)^2$.

The predicted normal FEV1 and reversibility values are recoded in the CRF as per the protocol assessment visits. The predicted normal FEV1 is based on the NHANES III equations as described in the protocol and Asian equation will be used for Asian race.

Reversible is defined as an increase in FEV1 of ≥12% and ≥200mL following administration of bronchodilator (albuterol/salbutamol) at any protocol assessment visit.

Non-reversible is defined as a post-bronchodilator (post-albuterol/salbutamol) increase in FEV1 of <200mL or increase that is <12% from pre-bronchodilator (pre-albuterol/salbutamol) FEV1.

A subject is considered achieved asthma control between Week 20 and Week 24 if he/she does not have a clinically significant exacerbation during this period between W20 and W24. The process for assessing clinically significant exacerbations of asthma is provided in Appendix9. Visit Windows.

Where a subject does not prematurely withdraw from the study, or the subject withdraws prematurely from the study at a scheduled visit, there are no plans to derive visit windows; visits will be used in the analyses as reported on the CRF.

For subjects prematurely withdrawing from the study, the EOS, unscheduled or IP discontinuation visit will initially be remapped to the next scheduled protocol specific assessment visit for each parameter, if the visit falls ±7 days of next scheduled planned visit (see below). Otherwise, the data will be remapped to the next planned scheduled visit. If there are more than one assessment associated with a particular visit interval, then the visit will be remapped to that with the closest target day. If subject having multiple records on same day for parameter (lab, ECG etc), then for continuous parameter data average value and for categorical parameter data, worst value will be presented. Please reframe the text accordingly.

| Visit | Target Day | Window (Days) |
|-------------------|------------|---------------|
| Visit 3 (Week 4) | 28 | 21 to 35 |
| Visit 4 (Week 8) | 56 | 49 to 63 |
| Visit 5 (Week 12) | 84 | 77 to 91 |
| Visit 6 (Week 16) | 112 | 105 to 119 |
| Visit 7 (Week 20) | 140 | 133 to 147 |

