| Visit 8 (Week 24) | 168 | 161 to 175 |

Unless otherwise stated, unscheduled visits will be included in the data listings only. If an unscheduled visit is present because of a visit/assessment missed due to COVID-19 factors, the unscheduled assessment may be used for remapping. The unscheduled visits may be used for summaries related to 'any time post baseline' assessment.

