11.1. EXTENT OF EXPOSURE

The total exposure to mepolizumab is calculated as the date of last dose of mepolizumab minus the date of first dose of mepolizumab plus 29 minus periods of interruptions (in days). Subjects who entered into induction phase but did not report any treatment dates will be categorized as having zero days of exposure. The extent of exposure will be summarized as number of injections administered and number of days on treatment.

Interruption period is calculated as the date of dose of mepolizumab after interruption period minus the date of interruption period of mepolizumab or the date of missed dose of mepolizumab.

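### The primary adverse-event window runs to 28 days after the last dose, but collection stops at an end-of-study visit that may fall earlier, so the primary incidences are slightly undercounted

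*Protocol*

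**What the plan says.** The risk window for the primary endpoint is fixed in Protocol section 3: "AEs will be defined as on-treatment between the first dose up to and including 28 days following the last dose of mepolizumab". SAP 7.2.4 repeats it: "On-treatment period = Date of first dose to Date of last dose plus 28 days inclusive".

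Collection is governed by Protocol 8.3.1: "All AEs will be collected from the start of intervention until the end of study visit". SAEs stop at the same visit. The section adds: "Investigators are not obligated to actively seek AEs or SAEs after the conclusion of the study participation". The exception is an SAE that the investigator happens to learn of later and considers related, which must be notified. SAP 11.2 likewise accounts for AEs only until the participant leaves the study.

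The synopsis puts the last dose at Week 20 and the end-of-study visit four weeks later, at Week 24. The Schedule of Activities gives treatment-period visits ±7 days. Protocol Appendix 10 gives the last visit the same tolerance and asks sites to make sure that the "end of study visit is completed within the prescribed window period (±7 Days". It does not say from which date those days are counted.

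No section requires the end-of-study visit to be at least 28 days after the last dose, and none schedules an AE contact at day 28.

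**The concern.** The risk window and the collection period have the same length only if both the Week 20 dose and the Week 24 visit fall at their nominal spacing. When the end-of-study visit comes sooner than 28 days after the last dose, the remaining days still belong to the primary window, but nobody is asked to look for events in them. A participant whose only event falls in those days is counted as event-free.

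The supplementary estimand does not recover these days. Under SAP 7.2.4 the post-treatment period begins 29 days after the last dose and ends at the end-of-study date, so for these participants it is empty.

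AE, SAE and AESI incidence is the primary endpoint and the only basis for the sample size. The study has one arm, so no comparator shares the same loss. The error can only lower the reported percentages.

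**Working it through.** **The plan's own figure.** For a true risk of 0.02 and n = 100, the chance of at least one affected participant is 1 − 0.98^100 = 0.8674. Protocol Table 3 prints 0.8673 and the text says greater than 86%, so the figure reproduces. The table assumes that the whole window is observed.

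**Shortest interval from last dose to end-of-study visit.**

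- Last-dose anchor. The synopsis places the visit four weeks after the last dose, and the Schedule of Activities note on immunogenicity ties that sample to four weeks from the last dose. With ±7 days the interval is 28 ± 7 = 21 to 35 days, so up to 28 − 21 = 7 days are unobserved.
- Week-0 anchor. The Schedule of Activities labels the visits Week 20 and Week 24. The corresponding day ranges appear in the SAP 7.2.8 table: "Visit 7 (Week 20) | 140 | 133 to 147" and "Visit 8 (Week 24) | 168 | 161 to 175". The interval is 161 − 147 = 14 to 175 − 133 = 42 days, so up to 28 − 14 = 14 days are unobserved.

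**How often, and by how much.** The documents give no distribution of visit timing. Assume visits fall evenly over the 15 whole days of a ±7-day window. A visit on day 28 is not short.

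- Last-dose anchor: the share seen before day 28 is 7/15 = 46.7%. Mean shortfall over all completers is (1 + 2 + … + 7)/15 = 28/15 = 1.87 days.
- Week-0 anchor, with the two visits independent: the share is 105/225 = 46.7%. Mean shortfall is Σ d(15 − d)/225 for d = 1 to 14, which is 560/225 = 2.49 days. The full 14-day loss occurs for 1/225 = 0.4%.
- The window runs to day 140 + 28 = 168 at nominal dosing. Hence 1.87/168 = 1.1% and 2.49/168 = 1.5%.

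If timing instead clusters around the target (normal weights on whole days, SD 3, cut at ±7), the share is 43% with a mean of 1.1 days (last-dose anchor), or 45% with 1.6 days (Week-0 anchor).

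**Effect on the detection probability.** Assume a constant hazard, so that the observable risk is 1 − 0.98^((window − missed)/window).

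| Case | Missed / window (days) | Observable risk | P(at least one in 100) |
|---|---|---|---|
| Nominal timing | 0 / 168 | 0.0200 | 0.867 |
| Even spread, last-dose anchor, average | 1.87 / 168 | 0.0198 | 0.864 |
| Even spread, Week-0 anchor, average | 2.49 / 168 | 0.0197 | 0.863 |
| Everyone at earliest visit, last-dose anchor | 7 / 168 (4.2%) | 0.0192 | 0.856 |
| Everyone at earliest visit, Week-0 anchor | 14 / 175 (8.0%) | 0.0184 | 0.844 |

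The last two rows are bounds, not forecasts.

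**The case against.** The strongest reply is that the gap is very small. At nominal timing nothing is missed. On average 1% to 2% of the window is lost, and the protocol's statement of better than 86% still holds on that average. A participant who has already had an AE is counted in the overall percentage whatever happens in the tail. All of this stands, and it limits the point to a cheap improvement.

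A reader might also infer more than the documents support:

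- **That the windows plainly permit a visit at day 14.** The SAP 7.2.8 table remaps visits of participants who withdraw prematurely. For the others, the SAP says that it does not plan to derive visit windows. The synopsis and the immunogenicity note favour counting from the last dose, which gives day 21. The week labels leave the Week-0 reading open, but it is not established.
- **That the missing days are those in which delayed reactions would appear.** The protocol's risk table says that systemic reactions usually occur within hours and can be delayed by several days. In completers the first 21 days after the last dose are always observed, or the first 14 on the wider reading.
- **That the exposure formula distorts the primary result.** SAP 11.1 calculates exposure as "the date of last dose of mepolizumab minus the date of first dose of mepolizumab plus 29", less interruptions. That credits the tail whether or not it was observed. However, exposure is summarised only descriptively, and the primary measure is counts and percentages of participants. No planned AE summary divides by exposure.
- **That events in the tail can never come to light.** Related SAEs learned of after discharge must still be notified. This duty does not extend to non-serious AEs, non-serious AESIs or unrelated SAEs.

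**Conclusion.** The mismatch holds. The primary window ends at day 28 after the last dose, collection ends at the end-of-study visit, and nothing makes the second at least as late as the first. Up to 7 days are unobserved if the visit is anchored to the last dose, and up to 14 if both visits are anchored to Week 0.

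Under evenly spread whole-day timing, about 47% of completers are affected. The mean loss over all completers is about 1.9 to 2.5 days, roughly 1.1% to 1.5% of the window. These averages rest on the assumed spread and, for the Week-0 reading, on independence of the two visits. The maximum losses rest only on the stated windows.

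The consequence is a small undercount of primary AE, SAE and AESI incidence, always in one direction. It does not undermine the sample-size table or the trial. The figures describe participants who receive the Week 20 dose and attend Visit 8. Those who stop treatment early but stay to Week 24 are followed past day 28. Those who leave the study early can lose more.

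**What to change.** 1. State in the Schedule of Activities whether the end-of-study window is counted from the last dose or from Week 0.
2. For participants who receive the Week 20 dose, require Visit 8 no earlier than 28 days after that dose, keeping the existing upper limit.
3. Where the visit nevertheless falls earlier, make one AE telephone contact at day 28, where consent allows.
4. In the SAP, report the number of participants observed for less than 28 days after the last dose.

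The cost is less room for the last visit. On a last-dose anchor the window becomes 28 to 35 days after the dose. On a Week-0 anchor with day 175 as the limit, a day-140 dose leaves days 168 to 175, and a day-147 dose leaves one permitted day (147 + 28 = 175). The alternative cost is one telephone call. Item 4 needs only the last-dose and end-of-study dates. The sample-size table and the SAP 11.1 exposure definition can stay as they are.
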